Inclusion/Exclusion criteria	
Inclusion criteria:
 
 • Patient is a minimum of 18 years of age • Independent of study participation, patient is a candidate for commercially available Persona, NexGen, or Vanguard knee components implanted in accordance with product labeling • Patient has participated in this study-related Informed Consent Process • Patient is willing and able to provide written Informed Consent by signing and dating the EC approved Informed Consent form • Patient is willing and able to complete scheduled study procedures and follow-up evaluations 
Exclusion criteria:
 
 • Patient is currently participating in any other surgical intervention studies or pain management studies • Patient has undergone contralateral UKA or TKA within the last 18 months • Hip pathology with significant bone loss (e.g. avascular necrosis of the femoral head with collapse, severe dysplasia of the femoral head or the acetabulum) • Hip pathology severely limiting range of motion (e.g. arthrodesis, severe contractures, chronic severe dislocation) • Patient is pregnant or considered a member of a protected population (e.g., prisoner, mentally incompetent, etc.) • Patient has previously received partial or total knee arthroplasty for the ipsilateral knee
Study Design	
Prospective, multicenter study, using Zimmer Biomet commercially available Persona, NexGen and Vanguard total knee implant system. Each consecutive, potential and eligible patient presenting as a candidate for primary knee arthroplasty will be offered study participation.
 
Selection process should be rotated on an equal basis. (eg. 5 Robotic TKA's followed by 5 Conventional TKA's and so on until enrolment is complete)

Clinical Phase	Post market
Sample Size	Maximum 8 EMEA sites, with participating surgeons contributing from 20 of each robotic and conventional knees per site. Maximum study enrolment of 240 subjects in total, including 40 subjects in the CT sub cohort
Length of Study	2,5 years (1,5 year enrolment with 1 year of follow-up). Follow-up visits at 6 weeks, 3 months and 1 year.

Materials and Methods	
Inclusion of 240 eligible subjects within maximum of 8 EMEA sites, divided into 2 groups (robotic and conventional group).
 
Sub cohort of 40 subject for CT assessment and analysis
 
Prospective follow up visit until 1 year post-operative with clinical and radiographic assessments.

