Data Collection	
Web based database (Electronic data capture system)

Statistical Reporting	
Performance will be evaluated for pain, function, health- related quality of life, and planned component position vs post-op component position. Data will be summarized descriptively additional to evaluation of data on surgical technique and instrumentation. Categorical data (e.g., gender or race) will be summarized using counts and percentages with 95% Confidence Interval (CI) limit over the time period of interest. Continuous data, such as age, will be summarized by using means, medians, SD, minimum, maximum, and 95% CI over the time period of interest. Implant survival and return to function will be summarized using a Kaplan-Meier method and presented with rates (as percentages) and CI.
 
Routine summaries of complication data is represented by frequencies and percentages. The sample size is based on a longitudinal data collection model and using functional outcomes as secondary endpoints.
 
The data from the CT sub cohort will detect for a difference in deviation from the initial alignment target proportions and presented with rates (as percentages) and CI.
 
Continuous data from pre and post-operative CT measurement will be summarized by using means, medians, SD, minimum, maximum and 95% CI over the time period of interest.

Scores/Performance Assessments	
Clinical performances are assessed by the following scores:
 
 • Oxford Knee Score • Objective Knee Assessment • Patient Satisfaction • EQ-5D • NRS Pain • FJS-12 
Radiographic performances are assessed by:
 
 • Radiographic imaging method pre- and post-operatively • Sub cohort for CT scan pre- and post-operatively
Standards	
The PMCF is compliant with the below:
 
 • The Declaration of Helsinki (DoH) - Ethical principles for medical research involving human subjects. [1] • ISO 14155: 2011 - Clinical investigation of medical devices for human subjects - Good clinical practice. [2]

References

- [1] WORLD MEDICAL ASSOCIATION DECLARATION OF HELSINKI, Ethical Principles for Medical Research Involving Human Subjects, Version October 2013.
- [2] ISO 14155:2011 International Standard for Clinical investigation of medical devices for human subjects -- Good clinical practice.

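### Technique is rotated in runs of consecutive cases, robotic first in the only example, and the analysis has no term for site, run or case order: common time trends need not cancel, and interval width is uncertain

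*Combined protocol and SAP*

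**What the plan says.** All of this is in the Study Synopsis.

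- **Allocation (Study Design).** "Each consecutive, potential and eligible patient presenting as a candidate for primary knee arthroplasty will be offered study participation". Technique is then assigned by rotation: "Selection process should be rotated on an equal basis". The only illustration, introduced as an example, is "5 Robotic TKA's followed by 5 Conventional TKA's and so on until enrolment is complete".
- **Size (Sample Size; Materials and Methods).** "Maximum study enrolment of 240 subjects in total, including 40 subjects in the CT sub cohort", with "participating surgeons contributing from 20 of each robotic and conventional knees per site" and at most 8 sites. Enrolment lasts 1.5 years (Length of Study).
- **Comparison (Study Objectives/Endpoints).** Comparing robotic with conventional instrumentation is the main purpose. Operative times are a named secondary endpoint.
- **Analysis (Statistical Reporting).** "Continuous data, such as age, will be summarized by using means, medians, SD, minimum, maximum, and 95% CI". Categorical data get counts and percentages with 95% intervals. For the CT sub cohort a difference is mentioned, shown as rates with an interval. No formula for a between-technique interval is given, and there is no term for site, surgeon, run, case order or calendar time.

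**The concern.** Under this rotation a technique is given to a run of consecutive patients, not to a patient. Two consequences follow, and the analysis text addresses neither.

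First, if every cycle opens with robotic cases, robotic cases come earlier throughout. Any change over time that affects both techniques alike, such as a theatre team settling into the study, then enters the robotic-minus-conventional difference as bias. Theatre time is the endpoint most exposed.

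Second, patients in one run may share staff and conditions. If those shared effects belong to the run, an interval built from patient-level SD and n ignores part of the error. At stake is whether a difference of a minute or two in theatre time, or a modest difference in scores, is read as a technique effect with more confidence than the design supports.

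**Working it through.** **Inputs from the synopsis.** 240 subjects; 18 months of enrolment; at most 8 sites; at least 20 + 20 = 40 knees per site; runs of 5 with robotic first (example only). **Assumed, because the documents give none:** the size and shape of any time trend, the run and site ICCs, even accrual, and one rotation per site. The plan states no bias, ICC or design effect that could be reproduced.

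**1. Cases per site and run length in time.** 6 × 40 = 240, whereas 8 × 40 = 320 exceeds the maximum. The per-site minimum therefore fits 240 only with 6 or fewer sites, so 40 cases per site is the main case. Accrual is 40/18 = 2.22 cases per site per month, and a run of 5 lasts 5/2.22 = 2.25 months. With 8 sites of 30 cases it would be 5/(30/18) = 3.0 months, but 30 per site is below the stated minimum. Either way there are 240/5 = 48 runs.

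**2. Order bias, robotic first.** Number a site's cases 0 to 39. The mean position is 17 for robotic and 22 for conventional, a gap of 5.

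- Linear fall of 10 minutes over the 40 cases: 5 × 10/39 = 1.28 minutes against robotic.
- Early excess of 15 minutes halving every 10 cases, 15 × 0.5^(i/10): the mean is 6.15 for robotic and 4.35 for conventional, a difference of 1.80 minutes against robotic.
- With 30 cases per site the figures are 5 × 10/29 = 1.72 and 2.24 minutes.

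A site that opens with conventional has the same bias with the opposite sign. With equal halves the mean is (1.28 − 1.28)/2 = 0, and likewise for the exponential trend. With a 4 to 2 split of six equal sites, 1.28 × (4 − 2)/6 = 0.43 minutes would remain.

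**3. Interval width when shared effects reset at each run.** Set total variance to 1, with site share s and run share b. Both techniques occur equally in each site, so site variance cancels from the difference but stays in a pooled patient-level standard error. Then

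true variance / pooled variance = (1 − s − b) + 5b = 1 − s + 4b, and coverage = 2Φ(1.96/√ratio) − 1.

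| Site share s | Run share b | Variance ratio | Coverage of nominal 95% |
|---|---|---|---|
| 0 | 0.01 | 1.04 | 94.5% |
| 0 | 0.05 | 1.20 | 92.6% |
| 0 | 0.10 | 1.40 | 90.2% |
| 0.05 | 0.01 | 0.99 | 95.1% |
| 0.10 | 0.02 | 0.98 | 95.2% |
| 0.05 | 0.05 | 1.15 | 93.2% |
| 0.10 | 0.10 | 1.30 | 91.4% |

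The pooled interval is too narrow only when 4b exceeds s. Simulation (10,000 replicates; 6 sites × 8 runs and 8 sites × 6 runs) agrees: about 92.7% at s = 0, b = 0.05, and 89.9% to 90.6% at s = 0, b = 0.10.

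Removing site variance removes the offset but leaves the run error. At s = 0.10, b = 0.10 the ratio becomes about (0.80 + 0.50)/0.90 = 1.44, and coverage is about 90%.

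**4. Interval width when period effects drift.** Let the shared effect have variance share p = 0.05 to 0.20 and within-site correlation exp(−|i − j|/L) between cases i and j, with L = 5 to 40 cases, 6 sites of 40 and no site variance. Adjacent runs of opposite technique then share most of the effect. The variance ratio runs from 1.024 (L = 5, p = 0.20) to 0.882 (L = 40, p = 0.20), giving coverage from about 94.7% to 96.3%. There is essentially no loss.

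**The case against.** A reader might infer that the planned intervals treat patients as independent and are therefore too narrow. The documents do not support that. They name no method for a robotic-versus-conventional interval; the sentence on continuous data describes a summary, with age as its example. Independence is inferred from the absence of any other term. The direction also depends on assumptions: undercoverage needs shared effects that change when the technique switches, and nothing in the synopsis says staff or conditions do so. If effects drift, or site variance stays in a pooled standard error, the interval is about right or too wide. This objection stands.

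The run of 5 and the robotic-first order are only an example, and the trends are assumed. That also stands, but no other rule is given, and sites may well follow the one they are shown. If several surgeons at a site rotate separately, the link between period and technique weakens. The larger figures (3.0 months, 1.7 and 2.2 minutes) need 30 cases per site, which conflicts with the stated minimum, so they are not relied on.

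Finally, the allocation is predictable and not randomised, which is the larger weakness. Neither a changed order nor a wider interval removes it.

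What the objection leaves untouched is the order bias: it requires no ICC, a wider interval would not remove it, and balancing the opening technique costs almost nothing.

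**Conclusion.** The point holds in a limited form. If sites follow the example, the fixed order lets a trend common to both techniques bias theatre time by about 1.3 minutes (linear 10-minute fall) to 1.8 minutes (15-minute early excess, half-life 10 cases) at 40 cases per site. Falling times work against robotic; rising times would favour it. The bias is small and scales with the assumed trend.

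The width of a pooled patient-level interval is uncertain, not shown to be too narrow. Coverage is about 93% to 90% if effects reset at run boundaries with run ICC 0.05 to 0.10 and no site variance; otherwise it is near or above nominal. No figure is given for the primary CT endpoint, because the synopsis does not say how the 40 CT subjects are spread over sites and runs.

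**What to change.** 1. **Opening order.** Have half of the sites open the rotation with conventional cases, keeping run length and theatre logistics as they are. This cancels trends common to sites if the two halves enrol similar numbers. It does not remove a learning curve confined to robotic cases. It can be set only before a site starts its rotation.
2. **Analysis.** Record case order and run number (per surgeon where surgeons rotate separately). Estimate robotic minus conventional within site, adjusted for case order. Report a run-level interval, from a random effect for run or run-clustered standard errors with a small-sample correction, as the main or a sensitivity analysis.

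The cost is a little extra recording (run number follows from case order), a line in the site instructions, a sentence or two in the analysis text and possibly somewhat wider intervals. The report should still state that allocation was predictable and non-random, since these changes do not cure that. The per-site minimum, the number of sites and the maximum of 240 should also be reconciled, because cases per site determine how large the order bias can be.

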ROSA Total Knee Post Market Study

A prospective, multicenter, EMEA post market clinical follow up
of the ROSA® Knee System

CME2019-24K

V3.0, 4 February 2020

STUDY SPONSOR

Zimmer GmbH Clinical Affairs

[name]

[name]

Switzerland

Study Synopsis

Title	ROSA Total Knee Post Market Study – a prospective, multi-center EMEA post market clinical follow up study for the ROSA Total knee system
Protocol Number	CME2019-24K
Sponsor	Zimmer GmbH
Manufacturer	Zimmer CAS, [name]
Study Device(s)	ROSA® Knee System
Study Objectives/Endpoints	
The main purpose of this study is to collect and compare clinical outcomes data using the commercially available ROSA Total Knee Robotic instrumentation and conventional instrumentation.
 
This will be achieved by assessing:
 
 1. Planned vs actual component positioning 2. Operative workflow efficiency 3. Patient safety based on incidence and frequency of adverse events 4. Clinical performance measured by overall pain and function, health- related quality of life data, and radiographic parameters. 
Primary endpoint: Evaluate the accuracy of implant alignment for ROSA total knee robotic instrumentation compared to conventional instrumentation, by measuring femoral rotation in the axial plane using pre op and post op CT assessments.
 
Secondary endpoints: Measure operative workflow efficiency by recording following time points during surgery: Patient in –and out time, incision – and incision closed time
 
Evaluate the change of the following scores between baseline and each post-operative follow up for performance and clinical benefits:
 
 • Oxford Knee Score • Objective Knee Assessment • Patient Satisfaction • EQ-5D • NRS Pain • FJS-12
Indications/Target population	Patients qualifying for primary total knee arthroplasty who meet the inclusion/exclusion criteria for study participation

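### The 1-year score changes have no repeated-measures model or missing-data rule, so early scores of subjects who leave go unused and outcome-related dropout can bias the result

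*Combined protocol and SAP*

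**What the plan says.** All of the text is in the Study Synopsis of the combined protocol and SAP.

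- **Purpose** (Study Objectives/Endpoints): to "collect and compare clinical outcomes data using the commercially available ROSA Total Knee Robotic instrumentation and conventional instrumentation".
- **Endpoint affected** (same row, secondary endpoints): "Evaluate the change of the following scores between baseline and each post-operative follow up for performance and clinical benefits". Six scores are listed.
- **Visits** (Length of Study): "Follow-up visits at 6 weeks, 3 months and 1 year".
- **Size and grouping** (Sample Size; Study Design): "Maximum study enrolment of 240 subjects in total, including 40 subjects in the CT sub cohort", and "Selection process should be rotated on an equal basis".
- **Analysis** (Statistical Reporting): "Data will be summarized descriptively additional to evaluation of data on surgical technique and instrumentation". For continuous variables: "Continuous data, such as age, will be summarized by using means, medians, SD, minimum, maximum, and 95% CI over the time period of interest".

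Two other phrases in Statistical Reporting might seem to deal with incomplete follow-up, but neither does. Kaplan-Meier is reserved for survivorship of the implant and return to function. The word longitudinal occurs only in the basis for the sample size: "The sample size is based on a longitudinal data collection model and using functional outcomes as secondary endpoints". The synopsis names no repeated-measures model, imputation, missing-data rule, analysis set, expected dropout or sensitivity analysis for the scores.

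**The concern.** A mean change at 1 year, with neither a model nor imputation behind it, can be computed only from subjects who have a 1-year value. A subject who leaves after 3 months counts in the two earlier summaries and then drops out of the 1-year one, although that subject's earlier scores carry information about the missing value. The subjects summarised can also differ from visit to visit, so part of an apparent gain between 3 months and 1 year may come from a change in who is being averaged.

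Two results are exposed, each under a condition:

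- **Within-group improvement** can be overstated if subjects doing badly are more likely to leave. For NRS Pain this means an overstated fall in pain.
- **The robotic-conventional difference** is biased if outcome-related dropout also differs between the groups. The error then favours the group that loses more subjects.

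Unequal dropout that is unrelated to outcome does not bias the comparison. Equal outcome-related dropout shifts both groups and leaves the difference about right.

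**Working it through.** **The plan's own figure.** The only sample-size figure is the maximum of 240. It cannot be reproduced, because no effect size, SD, power or dropout is given.

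**Inputs from the documents.** Visits at 6 weeks, 3 months and 1 year; two groups rotated equally; at most 240 subjects. I take this as 240 / 2 = 120 per group, assuming full enrolment and a 1:1 split.

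**Assumed inputs (not in the documents).**
- Score SD of 8.
- Correlation ρ = 0.6 between 3 months and 1 year.
- Correlation β = 0, 0.3 or 0.6 between baseline and the later scores.
- Dropout d before 1 year of 15% v 5%.
- Dropout depends on the 3-month score through a logistic curve. Slopes of 0.5 and 1.5 in log-odds per SD put leavers roughly 0.5 and 1.2 to 1.3 SD below stayers at 3 months. This gap is g.
- No true group difference.

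**Formula.** Subjects who stay have a 3-month mean d × g SD above that of all subjects. Their 1-year mean is therefore too high by ρ × d × g, and their baseline mean by β × d × g. The bias in mean change from baseline is

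bias = SD × (ρ − β) × d × g.

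The baseline term matters because the planned endpoint is a change, not a level.

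**Weaker dependence (slope 0.5).** g = 0.484 at 15% dropout and 0.494 at 5%.
- d × g = 0.15 × 0.484 = 0.0726 and 0.05 × 0.494 = 0.0247; difference 0.0479.
- β = 0: 8 × 0.6 × 0.0479 = 0.23 points.
- β = 0.3: 8 × 0.3 × 0.0479 = 0.115, about 0.12 points.
- β = 0.6: 0.

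**Stronger dependence (slope 1.5).** g = 1.168 at 15% and 1.297 at 5%.
- d × g = 0.1752 and 0.0649; difference 0.1103.
- β = 0: 8 × 0.6 × 0.1103 = 0.53 points.
- β = 0.3: 8 × 0.3 × 0.1103 = 0.265, about 0.27 points.
- β = 0.6: 0.

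**Equal 10% dropout.** The false difference is 0. With g = 0.489 to 1.217, each group's mean change is overstated by 8 × 0.6 × 0.10 × g = 0.23 to 0.58 points at β = 0, by half that at β = 0.3, and by 0 at β = 0.6.

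**Scale.** With SD 8 and 120 per group, the 95% CI half-width for a difference is 1.96 × 8 × √(2/120) = 2.02 points. The SD of a change score is 8 × √(2(1 − β)), which gives half-widths of 2.86, 2.40 and 1.81 for β = 0, 0.3 and 0.6. The largest bias, 0.53, is 26% of 2.02, or 19% of its own half-width of 2.86.

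**What using the earlier scores recovers.** In simulations with 120 per group, slope 1.5, 5% v 15% dropout, 3000 replicates and results in SD units of the 1-year outcome:

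| Dropout depends on | Correlation | Attendees only | Using 3-month scores |
|---|---|---|---|
| observed 3-month score | 0.5 | −0.056 | −0.001 |
| observed 3-month score | 0.7 | −0.079 | −0.002 |
| unseen 1-year score | 0.5 | −0.108 | −0.085 |
| unseen 1-year score | 0.7 | −0.110 | −0.062 |

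In the first two rows the bias is essentially removed. In the last two, (0.108 − 0.085)/0.108 = 21% and (0.110 − 0.062)/0.110 = 44% of it is removed.

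**The case against.** The case for leaving the plan alone is a fair one. This is a post-market follow-up that sets out to describe its data. The scores are secondary, and the primary endpoint is femoral rotation on CT. The use of attendees only is inferred from silence in a synopsis, and the quoted sentence gives age as its example and does not name the scores. The bias is small against the confidence interval and vanishes under some assumptions. A mixed model also does nothing about groups formed by rotation, with no randomisation described. On this view, a sentence on missing scores and a withdrawal table would be enough.

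Most of this stands as a limit on size and priority. It does not remove the point. The stated purpose is to compare the two techniques, the listed statistics allow no other way of computing a 1-year mean change, and the scores needed for a better estimate are already scheduled.

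A reader might also infer more than the documents support:

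- **That the plan prescribes an attendees-only analysis.** It contains no such rule. The reading follows from the absence of any model or imputation.
- **That subjects know their technique, so withdrawal will differ by group.** The synopsis says nothing about blinding either way and gives no dropout figures.
- **That a false difference of about half a point is to be expected.** That is the upper end of the range. It needs strong dependence of dropout on outcome and a baseline unrelated to later scores.

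**Conclusion.** The point holds as a conditional weakness in the analysis of a secondary endpoint. As written, a subject without a 1-year score contributes nothing to the 1-year result, whatever earlier scores exist. Whether this biases anything depends on dropout being related to outcome, and for the comparison on that dropout differing by group. The documents establish neither.

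Under the assumed values, the false difference in change from baseline lies between 0 and 0.53 points, most sensitive to the correlation of baseline with later scores and to the strength of the dropout mechanism. It would rarely change a conclusion by itself. The change is still worth making because it is cheap, and because settling the method before outcomes are seen prevents a choice made after the results are known. It should not be presented as a complete cure: if dropout follows the unseen 1-year outcome, more than half of the bias remained in the simulations.

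**What to change.** In Statistical Reporting:

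1. Keep the visit-wise descriptive tables.
2. For each score measured at several post-operative visits, add a mixed model for repeated measures with group, visit, group by visit, the baseline score where collected, and an unstructured covariance. Take the 1-year group means and their difference, with 95% CIs, from this model. Every subject with at least one post-operative score then contributes.
3. State the model's assumption that missingness is explained by the observed scores. Add a simple sensitivity analysis, for example one that makes the 1-year scores of leavers progressively worse than the model predicts, overall and in one group at a time.
4. Tabulate the number of withdrawals and the reasons by group and visit.

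The cost is a few sentences of statistical text and a little more analysis, with no extra visits or measurements; reasons for withdrawal must be recorded if they are not already. The model does not correct for non-random allocation, and the report should say so.

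### The robotic-versus-conventional comparison has no stated between-arm estimate and no adjustment for site, implant system or baseline, which costs some precision and leaves it open to imbalance

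*Combined protocol and SAP*

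**What the plan says.** All references are to the Study Synopsis in the combined protocol and SAP.

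- **Study Objectives/Endpoints:** the main purpose is comparative, robotic against conventional instrumentation. Secondary endpoints are four theatre time points and the change from baseline in six scores.
- **Study Design:** "Selection process should be rotated on an equal basis", with alternating runs of five as an example. The row does not call this randomisation and does not say whether the rotation runs within surgeon, within site or across the study. Three implant families are used: "using Zimmer Biomet commercially available Persona, NexGen and Vanguard total knee implant system". No row balances implant system between the groups.
- **Sample Size:** "Maximum 8 EMEA sites, with participating surgeons contributing from 20 of each robotic and conventional knees per site", and "Maximum study enrolment of 240 subjects in total, including 40 subjects in the CT sub cohort".
- **Statistical Reporting:** for continuous data, "Continuous data, such as age, will be summarized by using means, medians, SD, minimum, maximum, and 95% CI over the time period of interest". Categorical data get counts and percentages with a 95% CI, survival and return to function get Kaplan-Meier rates, and the CT sub-cohort gets rates with a CI. The row mentions no site, surgeon, implant or baseline term and no model for the between-group difference.
- **Data Collection:** a web-based database is named. Whether site and implant system are captured as analysis variables is not stated.

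**The concern.** A comparative aim needs a comparative estimate. The plan lists summaries, and a reader of the report would have to set one group's mean and CI beside the other's. That has three drawbacks.

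First, hospitals may differ in theatre times and scores. If each site supplies both groups in equal numbers, the design removes that variation from the difference, but an analysis that ignores site does not use this.

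Second, rotation gives no assurance of balance in the way that randomisation does. Implant candidacy is settled independently of the study (Inclusion/Exclusion criteria: "candidate for commercially available Persona, NexGen, or Vanguard knee components"), so implant mix can differ between groups, and so can baseline scores. No adjustment is stated for either.

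Third, two separate intervals are a poor tool for judging a difference. Requiring them not to overlap is a much stricter criterion than a CI for the difference itself.

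**Working it through.** **The plan's own figure.** The maximum of 240 cannot be re-derived, because no effect size, SD, rates, power or alpha is given. As a count, 6 sites × (20 + 20) = 240 agrees, but 8 × 40 = 320 exceeds the maximum. Both layouts that use all 240 are therefore taken: 6 sites × 20 per arm, and 8 sites × 15 per arm (240/8/2, below the stated 20). Either gives 120 per arm, assuming the rotation yields equal groups.

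**Precision of the difference.** Assume a shared site effect with variance share ICC, total SD = 1 and arms balanced within site. The site effect cancels from the difference.

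- Unadjusted variance as reported: 2/n. True variance: 2(1 − ICC)/n.
- Unadjusted half-width: 1.96 × √(2/120) = 0.253 SD.
- Excess width: 1/√(1 − ICC).

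| Assumed ICC | Adjusted half-width (SD) | Width ratio | Coverage of unadjusted 95% CI |
|---|---|---|---|
| 0.01 | 0.252 | 1.005 | 95.1% |
| 0.05 | 0.247 | 1.026 | 95.6% |
| 0.10 | 0.240 | 1.054 | 96.1% |

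The number of sites does not enter. Simulation (10,000 runs per setting) gave coverage of 95.1% to 95.7% for the unadjusted difference over the same ICC range. The unadjusted interval is valid here but slightly too wide.

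**Implant imbalance.** Bias = difference in implant share × implant effect. Both inputs are assumptions.

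- 10 points: 0.10 × 0.3 = 0.03 SD, and 0.10 × 0.5 = 0.05 SD.
- 20 points: 0.20 × 0.3 = 0.06 SD, and 0.20 × 0.5 = 0.10 SD.

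The standard error of the difference is √(2/120) = 0.129 SD. The 20-point case is thus 0.06/0.129 ≈ 0.5 to 0.10/0.129 ≈ 0.8 standard errors.

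**Two separate intervals.** The simple per-arm half-width is 1.96 × √(1/120) = 0.179 SD. For two such intervals not to overlap, the means must differ by 2 × 0.179 = 0.358 SD. A direct interval for the difference excludes zero at 0.253 SD. The ratio is 0.358/0.253 ≈ 1.41.

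**A robotic effect that varies by site.** Let ρ be an assumed site-by-arm variance share in each arm, with no shared site variance. With m subjects per arm per site, the true variance of the difference is 1 + (m − 1)ρ times the simple one, and coverage is 2Φ(1.96/√ratio) − 1.

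- 8 sites, m = 15: ρ = 0.01 gives ratio 1.14 and coverage 93.4%; ρ = 0.05 gives 1.70 and 86.7%.
- 6 sites, m = 20: ρ = 0.01 gives ratio 1.19 and coverage 92.8%; ρ = 0.05 gives 1.95 and 84.0%.

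This applies to inference beyond the participating sites. A main-effect site factor does not cure it, so it needs its own check.

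**The case against.** The strongest defence is that this is a descriptive post-market study and that the Statistical Reporting sentence is a general rule for continuous data, with age as its example. A better between-arm analysis is not ruled out. The loss of precision is small, and the unadjusted interval errs on the safe side when arms are balanced within site. The score endpoints are changes from baseline, so baseline is not ignored altogether.

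Much of that stands. The precision argument alone would not justify much effort. But a change score is not the same as adjustment for baseline: it removes the whole baseline difference, where a model removes only the part that predicts the outcome. Nothing stated deals with implant mix. And because the stated purpose is to compare, silence on how to compare matters more than it would in a single-group registry.

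A reader might go further and infer that the planned CIs are per-arm intervals that are too narrow because subjects are pooled across sites as if independent. With sites treated as a sample from a wider population, simple per-arm coverage would be 86.7% (8 sites) or 84.0% (6 sites) at an ICC of 0.05. The documents do not support that as a finding. The sentence mentions no arms, pooling or independence; no ICC is given; and the target of inference is not stated. If the target is the participating sites, simulated coverage was 95.1% to 95.8%, so there is no shortfall.

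Nor does ignoring implant system make intervals too narrow. The three systems are fixed strata, not sampled clusters, and matter only for imbalance and precision.

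**Conclusion.** The point holds for the between-arm comparison of theatre times and scores. The plan states a comparative purpose but only simple summaries, with no adjustment for site, implant or baseline. The certain part is that omission.

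The size is modest and conditional. An unadjusted interval is about 3% to 5% wider than needed at an assumed ICC of 0.05 to 0.10, provided arms are balanced within site; the per-site counts suggest this but the rotation rule does not state it. Bias is 0.06 to 0.10 SD under an assumed 20-point implant imbalance and a 0.3 to 0.5 SD implant effect, and proportionately less for smaller imbalances. The documents do not show that any imbalance will occur. The reason to change the plan is that a better analysis is available at almost no cost.

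**What to change.** Add the following to the Statistical Reporting row or a separate SAP.

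1. For theatre times and scores, report the robotic-minus-conventional difference with a 95% CI from a model with site and implant system as factors, plus the baseline value for scores that have one. If every site uses a single implant system, the site factor already carries implant and the implant term is dropped.
2. Keep per-arm means and SDs as description of the participating sites. Do not base the comparison on two separate per-arm CIs.
3. Fit a site-by-arm term as a sensitivity analysis and show the site-specific differences. With 6 to 8 sites this has little power, so an unremarkable result should not be read as proof of a constant effect.
4. In the 40-subject CT sub-cohort keep adjustment minimal: site only, where numbers allow.
5. State the unit within which the rotation runs, since the precision gain depends on it.

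Site-clustered standard errors are not recommended, because they are unreliable with 6 to 8 sites.

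The cost is slightly more analysis and a few degrees of freedom: 5 to 7 for site, 2 for implant and 1 for baseline, out of 238 (240 − 2) in the full cohort. Site and implant system must be confirmed as captured in the database. No added subjects or visits are needed.
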